7.3 Laboratory Test Abnormalities and other abnormal assessments as AEs or SAEs

Abnormal laboratory findings (e.g. clinical biochemistry, hematology) or other abnormal assessments (e.g. ECG, vital signs) that are judged by the investigator as clinically significant will be recorded as AEs or SAEs if they meet the definition of an AE, as defined in Section 7.1, or SAE as defined in Section 7.2.

Clinically significant abnormal laboratory findings or other abnormal assessments that are detected during the study or are present at baseline and significantly worsen following the start of the study will be reported as AEs or SAEs. However, clinically significant abnormal laboratory findings or other abnormal assessments that are associated with a disease reported in the medical history, unless judged by the investigator as more severe than expected for the participant's condition, or that are present or detected at the start of the study and do not worsen, will not be reported as AEs or SAEs.

Any treatment-emergent abnormal laboratory result which is clinically significant, i.e., meeting one or more of the following conditions, should be recorded as a single diagnosis on the AE page in the eCRF:

- Accompanied by clinical symptoms
- Leading to a change in IP (permanent or temporary discontinuation)
- Requiring a change in concomitant therapy (e.g. addition of, interruption of, discontinuation of, or any other change in a concomitant medication, therapy or treatment).

This applies to any protocol and non-protocol specified safety and efficacy laboratory result from tests performed after the first dose of IP, which falls outside the laboratory reference range and meets the clinical significance criteria.

This does not apply to any abnormal laboratory result which falls outside the laboratory reference range but which does not meet the clinical significance criteria (which will be analysed and reported as laboratory abnormalities) or those which are a result of an AE which has already been reported.

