7.8 Evaluating AEs and SAEs

7.8.1 Assessment of Severity

The investigator will make an assessment of severity for each AE and SAE reported during the study. The assessment will be based on the investigator's clinical judgment. The severity of each AE and SAE recorded in the eCRF should be assigned to one of the following categories:

Mild: An event that is easily tolerated by the participant, causing minimal discomfort, requiring minimal or no treatment and not interfering with everyday activities.

Moderate: An event that results in a low level of inconvenience or concern with the therapeutic measures. Moderate event may cause some interference with the normal everyday activities.

Severe: An event which interrupts a participant's everyday activities and may require systemic drug therapy or other treatment. Severe event is usually potentially life-threatening or incapacitating.

An AE that is assessed as severe should not be confused with an SAE. Severity is a category utilised for rating the intensity of an event; and both AEs and SAEs can be assessed as severe. An event is defined as "serious" when it meets one of the pre-defined outcomes as described in Section 7.2 "Definition of Serious Adverse Events".

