10.4.1 Adverse Events

Adverse events will be coded by body system as defined by the latest version of the MedDRAs, following classification of investigator assessments into MedDRA preferred terms.

Treatment-emergent adverse events, defined as adverse events with a start date on or after the first dose of IP will be tabulated by preferred term, body system, severity and treatment group.

Serious adverse events will be presented in a manner similar to that described for adverse events.

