10.4.2 Laboratory Data

All laboratory parameters will be summarized using descriptive statistics and presented by study visit and treatment group. Changes from Week 0 to post Week 0 visits will also be summarized.

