6.5.2 Adverse Events and Serious Adverse Events

6.5.2.1 Adverse Events

AEs will be coded by system organ class and body system according to the MedDRA dictionary (version 22.0).

The total number of TEAEs reported, the number and proportion of subjects experiencing at least one TEAE, at least one severe TEAE, at least one TEAE related to the study treatment, and at least one TEAE leading to drug withdrawal will be presented. In addition, number and proportion of subjects experiencing a treatment-emergent AE will be presented by system organ class and preferred term overall and for each treatment group.

A treatment-emergent AE will be defined as an AE with onset date on or after the date of first dose. If it is not possible to assess the timing of the start of the AE to the date of first dose due to incomplete AE onset date and/or incomplete date of first dose, the event will be assumed to be treatment-emergent.

All AEs will be listed but only treatment-emergent AEs will be summarized.

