6.5.6 Laboratory Parameters

Laboratory parameters, more specifically hematology and biochemistry parameters, will be summarized using descriptive statistics and presented by study visit (Screening, Baseline, Week 6 and Week 12) and treatment group.

All laboratory results will be listed.

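### The SAP reduces the protocol's adverse-event tabulation by severity to a single count of subjects with a severe event, and omits the promised laboratory changes from Week 0

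*SAP*

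**What the plan says.** **Adverse events.** Protocol 10.4.1 says that TEAEs "will be tabulated by preferred term, body system, severity and treatment group", and that serious events will be handled similarly. Protocol 7.8.1 supplies the grades (mild, moderate, severe): "The severity of each AE and SAE recorded in the eCRF should be assigned to one of the following categories".

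SAP 6.5.2.1 plans the number and proportion of subjects "experiencing a treatment-emergent AE will be presented by system organ class and preferred term overall and for each treatment group". Its only use of severity is in the overview, which counts subjects with "at least one severe TEAE, at least one TEAE related to the study treatment, and at least one TEAE leading to drug withdrawal". SAP 6.5.2.2 treats serious events like other adverse events, so the same reduction carries over to them.

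**Laboratory data.** Protocol 10.4.2 plans descriptive statistics by visit and group and adds: "Changes from Week 0 to post Week 0 visits will also be summarized". The synopsis makes the same commitment for Weeks 6 and 12. SAP 6.5.6 says that hematology and biochemistry parameters "will be summarized using descriptive statistics and presented by study visit (Screening, Baseline, Week 6 and Week 12) and treatment group", and that all results will be listed. It does not mention change from Week 0. Protocol 7.3, in its guidance on what to record as an adverse event, describes out-of-range results that are not clinically significant as results "which will be analysed and reported as laboratory abnormalities".

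**Precedence.** SAP section 1 states that the SAP overrides the protocol where they differ. It gives no reason for these reductions.

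**The concern.** The safety profile is a stated secondary objective, and the background section says that the trial is meant to help find the effective dosage of a new formulation. The daily tablet count rises from 3 to 6 to 12 across the cohorts (SAP 6.3.6). There is no data and safety monitoring board (protocol 9.2) and no formal safety testing (protocol 10.4, SAP 6.5), so the tolerability comparison between doses rests on the descriptive tables.

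One natural question for such tables is whether events become more troublesome as the dose rises, for instance whether complaints that are mild at the lowest dose become moderate at the highest. The protocol's tabulation would answer it. The SAP's overview line separates severe from everything else and pools mild with moderate, and no preferred term is shown by grade. For the laboratory data, group values at each visit do not give the within-subject change that the protocol promised.

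**Working it through.** The plan states no figure on this point, so the check is a comparison of the two documents, followed by one illustration.

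| Item | Protocol | SAP text | SAP section 7 |
|---|---|---|---|
| TEAEs by term and group | 10.4.1: yes | 6.5.2.1: yes | Table 3.2.2 |
| TEAEs by mild / moderate / severe | 10.4.1: yes | 6.5.2.1: severe count only | one line, in Table 3.2.1 |
| Serious events | 10.4.1: as for adverse events | 6.5.2.2: as for adverse events | Tables 3.2.3 and 3.2.4, neither titled by severity |
| Laboratory values by visit and group | 10.4.2: yes | 6.5.6: yes | Tables 3.6.1 and 3.6.2 |
| Laboratory change from Week 0 | 10.4.2 and synopsis: yes | 6.5.6: no | none named |
| Out-of-range results, not clinically significant | 7.3: parenthetical; 10.4.2: not mentioned | 6.5.6: no | none named |

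**Count of tables.** Six planned tables bear on tolerability by dose group: 3.1.1 (exposure), 3.1.2 (discontinuation) and 3.2.1 to 3.2.4 (adverse and serious events). None uses the three-level grade. None summarises laboratory abnormalities.

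**What the missing grade can conceal.** The documents give no adverse-event rates, so these are assumptions for illustration. Take 66 subjects per dose group (protocol 10.6), no severe events, and moderate events in 10% of one group and 25% of another:

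- 0.10 × 66 = 6.6, about 7 subjects
- 0.25 × 66 = 16.5, about 17 subjects

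Now let overall incidence be the same, 17 of 66 in both groups. The first group then has 7 subjects whose worst event is moderate and 17 − 7 = 10 whose worst event is mild. The second has 17 moderate and none mild.

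- SAP Tables 3.2.1 and 3.2.2: any TEAE 17 v 17, severe 0 v 0.
- Tabulation by severity: moderate 7 v 17, a difference of 10/66 = 15.2 percentage points.

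More generally, the any-TEAE and severe lines would read the same whatever the mild/moderate split. With 17 affected subjects per group, the unreported difference could lie anywhere from 0 to 17 subjects, or 0 to 17/66 = 25.8 percentage points. If overall incidence rose as well, from 7 to 17, the planned tables would show that rise.

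**Can the omitted laboratory changes be computed?** Yes, for most parameters. By the schedule of visits, hematology, AST, ALT, creatinine, LDH and CPK are measured at Weeks 0, 6 and 12, and glucose and insulin at Weeks 0 and 12. Bilirubin is taken at screening only, so it has no change from Week 0.

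**The case against.** The strongest reply is that this is a small reconciliation item. Safety is descriptive, the SAP is entitled to supersede the protocol, and SAP 6.2 promises descriptive statistics for all study variables by treatment group, which could be read to cover severity. Part of this stands: the point does not touch efficacy, and a deliberate simplification would be legitimate if stated. But the general sentence in SAP 6.2 does not restore the tabulation, because SAP 6.5.2.1 specifies the adverse-event outputs and section 7 names none by severity.

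A reader might also infer more than the documents support:

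- *Dose-related tolerability is invisible.* It is not. The treatment groups are the doses, and the six tables above remain, including TEAEs leading to withdrawal and treatment discontinuation. (The overview sentence does not itself say by group; that follows from SAP 6.2 and protocol 10.4.)
- *Moderate events are not reported.* They are counted in Tables 3.2.1 and 3.2.2, without their grade. A shift in severity could also show indirectly through withdrawals.
- *The severe count will be near zero in every arm.* Protocol 7.8.1 does say "Severe event is usually potentially life-threatening or incapacitating", but the preceding sentence is broader and covers events that interrupt daily activities. With no event rates in the documents, this is a forecast.
- *A single large laboratory rise would be hidden in a mean.* SAP 6.2 includes minimum and maximum, so an extreme value at a reported visit would normally show. All results are also listed, and clinically significant ones become adverse events under protocol 7.3.
- *The protocol promises a table of abnormality counts.* The words in protocol 7.3 are a parenthetical in recording guidance. They name no count or threshold, and protocol 10.4.2 plans none. The clear laboratory mismatch is the change from Week 0.

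**Conclusion.** The concern holds in a limited form. The SAP cuts a protocol-specified severity tabulation to one line, for both TEAEs and serious events, and gives no reason. What is lost is the mild/moderate distinction and any view of grade by preferred term. This matters most if overall incidence is similar across doses while severity shifts; whether that will happen cannot be judged from the documents. The SAP also omits laboratory change from Week 0, which is a plain mismatch with protocol 10.4.2. The missing summary of out-of-range results is a weaker point, since protocol 7.3 does not say what form the reporting should take.

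The conclusion rests on the SAP text and table titles. Table shells are not given, and the contents of Listing 5 (adverse events) are not specified, so whether severity appears there cannot be checked. The change is worth making because it is cheap and serves a stated objective; it does not bear on the primary analysis.

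**What to change.** - Add severity within system organ class and preferred term, by treatment group, to Tables 3.2.2 and 3.2.4, and say so in SAP 6.5.2.1. Maximum severity per subject (mild, moderate, severe) is one convenient form; protocol 10.4.1 asks only for severity.
- Add change from Week 0, by visit and group, to Tables 3.6.1 and 3.6.2 for every parameter measured at Week 0, and say so in SAP 6.5.6.
- Optionally, add a count by group of subjects with any post-dose value outside the laboratory reference range, which would give protocol 7.3 a concrete output.
- If the reductions are intended, state in the SAP that they depart from the protocol, and why.

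The cost is a few more programmed outputs from data already collected. No new data and no change to the efficacy analyses are needed.

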6.5.2.2 Serious Adverse Events

Serious adverse events will be presented in a manner similar to that described for adverse events.

6.5.3 Physical Examination

Physical examinations will include examination of various body systems and will be summarized by visit (Screening, Week 12) using frequencies and percentages, overall and by treatment group.

6.5.4 Vital Signs

Vital signs will be summarized by visit (Screening, Baseline, Week 6, Week 12) using descriptive statistics, overall and by treatment group.

6.5.5 Electrocardiogram

ECGs parameters will be summarized by visit (Screening, Week 12) using descriptive statistics, overall and by treatment group.

6.5.6 Laboratory Parameters

Laboratory parameters, more specifically hematology and biochemistry parameters, will be summarized using descriptive statistics and presented by study visit (Screening, Baseline, Week 6 and Week 12) and treatment group.

All laboratory results will be listed.

7 SUMMARY TABLES, FIGURES AND LISTINGS

| | |
|---|---|
| 1 Study subject | |
| 1.1 Subject disposition | |
| Table 1.1.1 | Subject disposition |
| Table 1.1.2 | Datasets analyzed |
| Table 1.1.3 | Protocol deviation, ITT population |
| | |
| 1.2 Demographic and baseline characteristics | |
| Table 1.2.1 | Summary of demographics, ITT population |
| Table 1.2.2 | Summary of medical history, ITT population |
| | |
| 1.3 Prior and concomitant medication | |
| Table 1.3.1 | Summary of medication at randomization, ITT Population |
| Table 1.3.2 | Summary of prior and concomitant medication, ITT Population |
| | |
| 1.4 Treatment compliance | |
| Table 1.4.1 | Summary of treatment compliance, ITT population |

| | |
|---------------------------------|---|
| 2 Efficacy analysis | |
| 2.1 Primary analysis | |
| Table 2.1.1 | Summary of and statistical analysis for change in direct-measured LDL-C (mg/dL), ITT population |
| Table 2.1.2 | Summary of and statistical analysis for change in direct-measured LDL-C (mg/dL), PP population |
| Table 2.1.3 | Summary of and statistical analysis for change in direct-measured LDL-C (mg/dL), Modified PP population with compliance criteria set to 70% |
| | |
| 2.2 Secondary analysis | |
| Table 2.2.1 | Summary of and statistical analysis for change in TC (mmol/L), ITT population |
| Table 2.2.2 | Summary of and statistical analysis for change in non-HDL-C (mmol/L), ITT population |
| Table 2.2.3 | Summary of and statistical analysis for change in small LDL subclass particle concentration (nmol/L), ITT population |
| Table 2.2.4 | Summary of and statistical analysis for change in hsCRP (mg/L), ITT population |
| Table 2.2.5 | Summary of and statistical analysis for change in VLDL-C (mmol/L), ITT population |
| Table 2.2.6 | Summary of and statistical analysis for change in Apo B (g/L), ITT population |
| | |
| 2.3 Exploratory analysis | |

| | |
|-----------------------|---|
| Table 2.3.1 | Summary of and statistical analysis for change in HDL-C (mmol/L), ITT population |
| Table 2.3.2 | Summary of and statistical analysis for change in TG (mmol/L), ITT population |
| Table 2.3.3 | Summary of and statistical analysis for change in Lp(a) (g/L), ITT population |
| Table 2.3.4 | Summary of and statistical analysis for change in HbA1c (%), ITT population |
| | |
| 2.4 Subgroup analysis | |
| Table 2.4.1 | Summary of and statistical analysis for change in direct-measured LDL-C (mg/dL) broken down by severity of hypercholesterolemia (below median or greater or equal to median of direct-measured LDL-C at baseline), ITT population |
| Table 2.4.2 | Summary of and statistical analysis for change in direct-measured LDL-C (mg/dL) broken down by severity of hypercholesterolemia (according to quartiles of direct-measured LDL-C at baseline), ITT population |
| Table 2.4.3 | Summary of and statistical analysis for change in direct-measured LDL-C (mg/dL) broken down by sex (male or female), ITT population |
| Table 2.4.4 | Summary of and statistical analysis for change in direct-measured LDL-C (mg/dL) broken down by diabetes (yes or no), ITT population |
| Table 2.4.5 | Summary of and statistical analysis for change in direct-measured LDL-C (mg/dL) broken down by hypertension (yes or no), ITT population |
| Table 2.4.6 | Summary of and statistical analysis for change in direct-measured LDL-C (mg/dL) broken down by age (<65 years or ≥ 65 years), ITT population |
| Table 2.4.7 | Summary of and statistical analysis for change in direct-measured LDL-C (mg/dL) broken down by age (according to quartiles), ITT population |
| Table 2.4.8 | Summary of and statistical analysis for change in direct-measured LDL-C (mg/dL) broken down by statin treatment at baseline (yes or no), ITT population |

| | |
|---|---|
| 3 Safety analysis | |
| 3.1 Treatment exposure | |
| Table 3.1.1 | Summary of extent of exposure, safety population |
| Table 3.1.2 | Summary of discontinuation of study treatment, safety population |
| | |
| 3.2 Adverse events and serious adverse events | |
| Table 3.2.1 | Overall summary of treatment emergent adverse events (TEAE), safety population |
| Table 3.2.2 | Summary of treatment emergent adverse events (TEAE) by system organ class and preferred term, safety population |
| Table 3.2.3 | Overall summary of treatment emergent serious adverse events (TESAE), safety population |

| | |
|----------------------------------|--|
| Table 3.2.4 | Summary of treatment emergent serious adverse events (TESAE) by system organ class and preferred term, safety population |
| | |
| 3.3 Physical examination | |
| Table 3.3.1 | Summary of physical examination, safety population |
| | |
| 3.4 Vital signs | |
| Table 3.4.1 | Summary of vital signs, safety population |
| | |
| 3.5 Electrocardiogram | |
| Table 3.5.1 | Summary of ECG, safety population |
| | |
| 3.6 Laboratory parameters | |
| Table 3.6.1 | Summary of hematology laboratory results, safety population |
| Table 3.6.2 | Summary of biochemistry laboratory results, safety population |

| | |
|----------------|--|
| Figures | |
| Figure 1 | Subject disposition (flow chart) |
| Figure 2 | Plot of predicted change from Week 0 to Week 12 in direct-measured LDL-C (mg/dL) with 95% CIs against dose level, ITT population |

| | |
|-----------------|------------------------|
| Listings | |
| Listing 1 | Subject disposition |
| Listing 2 | Datasets analyzed |
| Listing 3 | Protocol deviations |
| Listing 4 | Demographics |
| Listing 5 | Adverse events |
| Listing 6 | Serious adverse events |
| Listing 7 | Laboratory results |
| Listing 8 | Deaths |

8 REFERENCES

Not applicable.

9 APPENDICES

9.1 Appendix 1 - Schedule of visits

| Procedure/Visit | Screening Period (V1) | Randomization Baseline Visit (V2) | Visit 3 (V3) | End of Treatment Visit (V4) | Safety Follow-up Visit (V5) (telephone) |
|---|--------------------------|---|----------------------|-----------------------------------|--|
| | Week -1 Up to 7 days | Week 0 | Week 6 (± 5 days) | Week 12 (± 5 days) | Week 14 (± 5 days) |
| Informed consent form | X | | | | |
| Inclusion & Exclusion criteria | X | X | | | |
| Medical History | X | X | | | |
| Demographics | X | | | | |
| Physical examination | X | | | X | |
| Vital signs (blood pressure, pulse) | X | X | X | X | |
| Height | X | | | | |
| Weight | X | | | X | |
| Dietary counselling including alcohol consumption, and timing of statin vs. IP intake | X | X | X | | |
| Check compliance on statin and IP | | | X | X | |
| 12-Lead ECG | X | | | X | |
| Hematology | X | X | X | X | |
| AST, ALT, Creatinine | X | X | X | X | |
| Bilirubin | X | | | | |
| LDH, CPK | | X | X | X | |
| TG, TC, LDL-C, HDL-C | X | X | X | X | |
| LDL-C (direct-measured), VLDL-C, apo-B, Lp(a), non-HDL-C, small low-density lipoprotein (LDL) subclass particle concentration | | X | X | X | |
| HbA1c, Insulin, Glucose and hsCRP | | X | | X | |
| Concomitant medication | X | X | X | X | |
| Pregnancy test* | X* | X* | | | |
| Randomization | | X | | | |
| IP dispensing | | X | X | | |
| Adverse Events | X** | X** | X** | X** | X** |

*Female patients of childbearing potential will have a urine pregnancy test performed at the screening visit and at randomization (visit 2)

**Serious Adverse Events (SAEs) are captured from the time of consent through to week 14 safety Follow up phone call. AEs are captured between the time of randomization up to the last dose IP taken.

9.2 Appendix 2 - Reporting windows for laboratory parameters

Number of days between a laboratory assessment and randomization will be calculated (date of assessment – date of randomization + 1 day), compared to the lab reporting window below, and the assessment will be assigned to the corresponding visit.

| VISIT | SCHEDULED VISIT | SCHEDULED DAY | SCHEDULED WINDOW (± DAYS) | SCHEDULED WINDOW (DAYS) | LAB REPORTING WINDOW (DAYS) |
|-------|--------------------------|---------------|-----------------------------------|-------------------------|-----------------------------|
| V1 | Screening | | Up to 7 days before randomization | <1 | <1 |
| V2 | Baseline (randomization) | 1 | | 1 | 1 to 2 |
| V3 | Week 6 | 42 | ±5 | 37 to 47 | 3 to 63 |
| V4 | Week 12 | 84 | ±5 | 79 to 89 | ≥64 |

Notes:

The algorithm chooses the mid-point between consecutive scheduled visits and so achieves that no gaps between reporting windows occur, and that reporting windows correspond to the schedule of assessments.

In cases where more than one non missing assessment falls within the same window, the closest assessment will be chosen.

The LAB reporting window for baseline visit include day 2 because some subjects were randomized on scheduled day 1 but laboratory parameters were taken only the next day, where day 2 is the day of first dose.

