5.6 Laboratory Parameters

A full clinical laboratory profile including hematology, biochemistry, lipids and other analyses will be performed during the study. Laboratory data will be transferred electronically by the Dynacare central lab. Blood samples are to be collected at Screening, Baseline, Week 6, Week 12 and at some unscheduled visits if it is necessary to repeat testing following abnormal laboratory results. Here is the list of the collected laboratory assessment:

Screening (Visit 1): The following screening laboratory assessments are to be performed during the screening period for the determination of study eligibility and the patient's current medical state at the time of study entry:

| | Determinations | |
|---|--|---|
| Hematology | RBC | |
| | Hemoglobin | |
| | Hematocrit | |
| | WBC | |
| | Platelet Count | |
| | Differential (to be performed only if WBC is abnormal) | Neutrophils Lymphocytes Monocytes Eosinophils Basophils |
| Biochemistry | AST | |
| | ALT | |
| | Bilirubin | |
| | Creatinine | |
| | eGFR | |
| Lipids | Triglycerides | |
| | Total cholesterol | |
| | LDL-Cholesterol | |
| | HDL-Cholesterol | |
| Urine (only for females of childbearing potential) | Human chorionic gonadotropin (hCG) urine pregnancy test | |

Baseline and Treatment Period (Visits 2, 3, and 4)

| Determinations | | |
|---|--|---|
| Hematology | RBC | |
| | Hemoglobin | |
| | Hematocrit | |
| | WBC | |
| | Platelet Count | |
| | Differential (to be performed only if WBC is abnormal) | Neutrophils Lymphocytes Monocytes Eosinophils Basophils |
| Biochemistry | AST | |
| | ALT | |
| | LDH | |
| | CPK | |
| | Creatinine | |
| | eGFR | |
| | Glucose (fasting) (at visit 2 and 4 only) | |
| | Insulin (fasting) (at visit 2 and 4 only) | |
| | HbA1c (at visit 2 and 4 only) | |
| | hs-CRP (at visit 2 and 4 only) | |
| Lipids / Other | Triglycerides | |
| | Total cholesterol | |
| | LDL-Cholesterol (direct-measured) | |
| | HDL-Cholesterol | |
| | VLDL Cholesterol | |
| | Apolipoprotein B (apo B) | |
| | Lipoprotein (a) [Lp(a)] | |
| | Non-HDL-C | |
| | small low-density lipoprotein (LDL) subclass particle concentration | |
| Urine (only for females of childbearing potential) | Human chorionic gonadotropin (hCG) urine pregnancy test (Visit 2 only) | |

Female patients of childbearing potential will have a urine pregnancy test performed at the Screening visit and at Baseline.

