6.2 Statistical Considerations

This is a randomized, parallel study with four treatment groups (placebo, beta-glucan 1.5 g, beta-glucan 3 g and beta-glucan 6 g). The statistical analysis will focus on the comparisons of the three active groups vs. placebo.

Descriptive statistics of all study variables will be presented overall and broken down by treatment group. Number of observations, mean, standard deviation, median, minimum and maximum will be presented for continuous variables. Count and proportion will be displayed for categorical variables.

Basic assumptions of the proposed analyses will be checked and data transformation or other analyses could be done if appropriate. For example, as some endpoints are likely to be skewed (ex. triglycerides, hsCRP), log-transformation might be used, in which case descriptive statistics would also include geometric means.

Laboratory parameters will be assigned to visits based on number of days from randomization and not based on scheduled visit at which the measurement was made. The time windows that will be used to assign measurements to visits are given in Appendix 2.

Values entered as less than a specified value will be considered as the specified value divided by 2 (e.g. entered value <0.2 will be analyzed as 0.1). Values entered as BLQ (Below Limit of Quantification) will be considered as the limit of quantification divided by 2. Values entered as more than a specified value will be considered as the specified value.

All statistical tests will be two-sided. Tests involving the comparisons of the active groups vs. placebo for the primary endpoint will be conducted at the 0.0167 significance level. All other tests will be considered secondary or exploratory and will be conducted at the 0.05 significance level.

No interim analysis on efficacy endpoints is planned for this study.

Statistical analyses will be done using SAS version 9.4 or higher.

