6.2.1 Handling of Missing Data

For efficacy laboratory endpoints, the screening value will be taken if the baseline value is missing.

In addition, the proposed statistical analysis will account for all available data and will not disregard subjects with missing data at either Week 6 or Week 12. However, in subjects who will only have a baseline measurement, the last observation carried forward approach will be used.

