6.4.1 Primary Analysis

The primary endpoint is the change from Week 0 to Week 12 in direct-measured LDL-C. The changes, as well as the LDL-C values at each study visit, will be summarized with descriptive statistics.

The primary endpoint will be compared between treatment groups using a repeated measures analysis of covariance (ANCOVA) model.. More specifically, the dependent variable will be the change from Week 0 in LDL-C (change calculated as post Week 0 level – Week 0 level) the model will include treatment group, time (Week 6 and Week 12) and treatment group x time interaction as well as the covariates of Week 0 value of LDL-C and Week 0 value of LDL-C x time interaction. An unstructured covariance structure will be

used to model the within-patient errors and the Kenward-Roger approximation will be used to estimate denominator degrees of freedom. Contrasts under this model will allow for the three main comparisons: placebo vs. beta-glucan 1.5 g, placebo vs. beta-glucan 3 g and placebo vs. beta-glucan 6 g. More specifically, the following hypotheses will be tested:

$$H_0: \Delta_{W12,\text{placebo}} = \Delta_{W12,1.5g} \quad \text{vs.} \quad H_1: \Delta_{W12,\text{placebo}} \neq \Delta_{W12,1.5g}$$

$$H_0: \Delta_{W12,\text{placebo}} = \Delta_{W12,3g} \quad \text{vs.} \quad H_1: \Delta_{W12,\text{placebo}} \neq \Delta_{W12,3g}$$

$$H_0: \Delta_{W12,\text{placebo}} = \Delta_{W12,6g} \quad \text{vs.} \quad H_1: \Delta_{W12,\text{placebo}} \neq \Delta_{W12,6g}$$

where $\Delta_{W12,\text{placebo}}$, $\Delta_{W12,1.5g}$, $\Delta_{W12,3g}$ and $\Delta_{W12,6g}$ are respectively the mean change from Week 0 to Week 12 in LDL-C in the placebo, beta-glucan 1.5 g, beta-glucan 3 g and beta-glucan 6 g group.

All sets of hypotheses will be tested at the 0.0167 significance level to maintain the overall type I error to 0.05 for the primary endpoint. These tests will be considered as the primary analysis of the study.

For illustrative purposes, changes within groups will be tested at the 0.05 significance level. Estimates of the changes within groups and of the between-group differences will also be presented along with 95% confidence intervals.

The same ANCOVA model will also allow for the examination of the change from Week 0 to Week 6 in LDL-C. In other words, the hypotheses described above will also be tested at Week 6 at the 0.05 significance level for illustrative purposes.

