Because the SAS procedure PROC MIXED will be used, subjects with missing data at a given study visit will not be excluded from the analysis.

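### Does opening the Week 6 laboratory window on day 3, against the SAP's own mid-point note, distort the Week 12 comparison?

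*SAP*

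**What the plan says.** SAP 6.2 sets the principle: "Laboratory parameters will be assigned to visits based on number of days from randomization and not based on scheduled visit". Appendix 2 applies it by computing the study day of each sample and looking it up in a table. That table gives Baseline days 1 to 2, Week 6 days 3 to 63 and Week 12 day 64 onward, for scheduled days 1, 42 and 84.

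Three notes stand beneath the table:

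- On how the cuts were made: "The algorithm chooses the mid-point between consecutive scheduled visits and so achieves that no gaps between reporting windows occur".
- On ties: "In cases where more than one non missing assessment falls within the same window, the closest assessment will be chosen".
- On Baseline: "The LAB reporting window for baseline visit include day 2 because some subjects were randomized on scheduled day 1", with the blood drawn the next day, which was then the day of first dose.

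Two rules elsewhere decide what happens to a subject with little follow-up. SAP 6.4.1 says of the mixed model that "subjects with missing data at a given study visit will not be excluded from the analysis". SAP 6.2.1 adds that "in subjects who will only have a baseline measurement, the last observation carried forward approach will be used".

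**The concern.** The note and the table disagree about the lower edge of Week 6. A mid-point rule would open the window at day 22; the table opens it at day 3. The Baseline note explains why Baseline ends at day 2, but nothing says the mid-point rule was set aside for Week 6.

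The tie rule helps only when a window holds two or more samples, so a lone sample from, say, day 10 becomes the Week 6 value. Such a sample could come from an early-termination visit: Protocol 6.11 encourages the Week 12 procedures, which include direct LDL-C. It could also come from a repeat test, since SAP 5.6 allows blood draws "at some unscheduled visits if it is necessary to repeat testing following abnormal laboratory results".

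A few days of product would then be read as a six-week response. Because the two visits are modelled jointly with an unstructured covariance, that value also feeds the estimated Week 12 mean. This is the primary endpoint, so an ambiguous visit rule deserves a check.

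**Working it through.** **Reproducing the cuts.** (42 + 84)/2 = 63, so Week 6 ends on day 63 and Week 12 starts on day 64, as in the table. (1 + 42)/2 = 21.5, which would start Week 6 on day 22, not day 3. Numbering the visits as days 43 and 85 gives 22 and 64, so that does not explain day 3 either. The days assigned against the note are 3 to 21, which is 19 days.

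**Where day 3 comes from.** Baseline closes at day 2 and the note also promises no gaps, so Week 6 must open at day 3. A literal mid-point would instead make on-treatment samples up to day 21 eligible as Baseline.

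**Effect on the Week 12 difference.** Inputs from SAP 6.1: mean change −0.30 mmol/L on placebo and −0.60 on active (difference 0.30), SD 0.50, 60 evaluable and 66 randomised per group. Standard error = 0.50 × √(2/60) = 0.0913.

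Assumptions, not in the documents: the planned means are reached by Week 6; the slope *b* of Week 12 on Week 6 is 0.4 to 0.8; a share *f* of the Week 6 change is present at the early sample.

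With dropout after the first follow-up value, the model's Week 12 arm mean is the completers' Week 12 mean plus *b* times the gap between the Week 6 mean of all subjects and that of completers. With n_A and n_P lone early samples in the active and placebo arms:

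shrinkage = *b* (1 − *f*) (0.60 n_A − 0.30 n_P) / 66

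At *f* = 0 (a negative value means the difference is inflated):

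| n_A, n_P | *b* = 0.4 | *b* = 0.6 | *b* = 0.8 | Size as % of SE |
|---|---|---|---|---|
| 1, 0 | 0.0036 | 0.0055 | 0.0073 | 4–8 |
| 0, 1 | −0.0018 | −0.0027 | −0.0036 | 2–4 |
| 1, 1 | 0.0018 | 0.0027 | 0.0036 | 2–4 |
| 2, 0 | 0.0073 | 0.0109 | 0.0145 | 8–16 |

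At *f* = 0.5 every entry halves. With equal counts and no true effect the shift is zero. Dividing by the 61 or 62 subjects who contribute data, rather than 66, raises the entries by 6 to 8%.

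**Upper bound.** Suppose all of the expected 9% loss in each arm had only a day 3 to 21 sample with no response yet, and *b* = 0.8. The attenuation is 0.8 × 0.09 × 0.30 = 0.0216 mmol/L (7.2% of 0.30), and power at 60 per group falls from 80.3% to 73.2%. This is a ceiling, not a forecast.

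**Effect on Week 6.** Here the value enters directly: 0.60/66 = 0.0091 per active subject and 0.30/66 = 0.0045 per placebo subject. SAP 6.4.1 labels the Week 6 test illustrative.

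**Would starting at day 22 do better?** Take 60 completers per arm plus two lone early samples on active, *b* = 0.6, *f* = 0:

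- As written: 0.30 − 0.6 × 2 × 0.60/62 = 0.288.
- Window moved, SAP 6.2.1 unchanged: the two become baseline-only and, if zero change is carried to Week 12, the difference is 0.60 × 60/62 − 0.30 = 0.281.
- Window moved and carry-forward removed: 0.300, which is correct only if those subjects are missing at random.

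A simulation of this case gave the same three values. If the two early leavers truly show no change at Week 12, the intention-to-treat difference is itself 0.281. If they settle at the placebo change, it is 0.30 × 60/62 = 0.290. In both cases 0.288 is nearer the truth than 0.300.

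**The case for a change.** The strongest case for a change is that an analyst who codes from the note and one who codes from the table would build different primary datasets, and that choosing between them after unblinding would be a data-informed choice. Correcting this before lock looks cheap: one table row, one note, one sentence on missing data and one sensitivity run. The exposed group is also slightly wider than early leavers. It includes a subject with a Week 12 sample whose only draw in days 3 to 63 was early.

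The mismatch in wording stands. The two-dataset argument does not carry far, because the opening instruction of Appendix 2 sends the analyst to the table, which is complete and has no gap or overlap; the mid-point sentence describes it. The low cost is also doubtful. Moving the window alone makes matters worse under SAP 6.2.1. Pairing it with removal of carry-forward changes the handling of every baseline-only subject, which is a larger question that this point does not settle.

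The exposed group is narrow. Subjects who stop product but stay in the study keep their visits (Protocol 4.3 and 5.5), exit procedures are only encouraged, and Protocol 6.10 lists only medication changes and adverse events for unscheduled visits. Where a Week 12 sample exists, it enters the Week 12 estimate directly.

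**Conclusion.** This is a clerical slip in an explanatory note. The mid-point description fits the Week 6/Week 12 cut only, and the other cut follows from closing Baseline at day 2 without leaving a gap. Adding that exception to the note would be tidier, but it would alter no assignment and no result.

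Under the stated assumptions the Week 12 difference moves by 0.001 to 0.004 mmol/L with one lone early sample in each arm (1 to 4% of the standard error, allowing for *f* of 0 to 0.5). With two on active and none on placebo it moves by 0.004 to 0.015 (4 to 16%). The direction depends on counts by arm, which the documents do not give and which may be zero. The slope and the time course of response are also assumptions.

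The alternative window is a trade-off with no clear gain: it helps only if early leavers are missing at random, and otherwise it can sit further from the intention-to-treat effect than the plan as written. The window and the missing-data rule can stay as they are on this point.
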